6.2 Sponsor's Responsibilities

The Sponsor of the program is Hill-Rom Company, Inc. The Sponsor's, responsibilities are itemized below.

- The Sponsor is responsible for implementing and maintaining quality assurance and quality control systems with written standard operating procedures (SOPs) to ensure that studies are conducted and that the data are generated, documented, and reported in compliance with the protocol, GCPs and applicable regulatory requirements. The Sponsor is responsible for securing an agreement from all involved parties to ensure direct access to all study-related sites, source documents, and reports for the purpose of monitoring and auditing.
- The Sponsor may transfer any or all of the study-related duties and functions to a Contract Research Organization (CRO), but the ultimate responsibility for the quality and integrity of the data resides with the Sponsor.
- The Sponsor should use an unambiguous patient identification code that allows for de-identification of all the data reported for each patient.

Hill-Rom®	Evaluation of a practice change to include The MetaNeb® System to reduce postoperative pulmonary complications	Page 27 of 31
CBI	8 September 2016	Rev C Protocol #: CR-RR2015- 001

- The Sponsor should retain the essential documents as required by the applicable regulatory requirements. Records must be maintained for a period of three years after the latter of the following dates: the date the study is completed/terminated or the date of the last regulatory approval.
- The Sponsor should ensure the Investigator(s) selected for the study have the proper qualifications, training, and resources to perform the study adequately.
- The Sponsor shall provide the Investigator(s) with a protocol and an Investigator Brochure (or equivalent documentation) and allow sufficient time for the Investigator to review the information provided.
- The Sponsor should ensure timely delivery of the Device(s) to the Investigator(s); maintain records that document shipment, receipt, disposition, return and destruction (if applicable) of the Devices; maintain a system for retrieving Devices and documenting this retrieval; maintain a system for the disposition of unused Device(s) and for the documentation of this disposition.
- The Sponsor should ensure that it is specified in the protocol or other written agreement that the Investigator(s)/Institution(s) provide direct access to source documents for study-related monitoring, audits, IRB review, and regulatory inspection. The Sponsor should verify that each patient has consented in writing, to direct access to his/her original medical records for study-related monitoring, audit, IRB review and regulatory inspection, or that informed consent has been waived.
- The Sponsor is responsible for submitting reports of all recalls and device disposition to the IRB and the FDA.

7.0 Administrative Study Information

7.1 Pre-Study Site Visit

The Sponsor will visit the site and meet with the Investigator(s) to assess and confirm the site's ability to perform the study, store study equipment, and recruit patients.

Hill-Rom®	Evaluation of a practice change to include The MetaNeb® System to reduce postoperative pulmonary complications	Page 28 of 31
CBI	8 September 2016	Rev C Protocol #: CR-RR2015-001

7.2 Institutional Review

Prior to study initiation, the appropriate IRB must approve the observational study. It is the responsibility of the Investigators, in collaboration with the Sponsor, to provide the IRB with all necessary information to satisfy the individual Institution's requirements.

7.3 Investigator Records and Reports

Where required by applicable regulatory requirements, an investigator signatory will be obtained for the acceptance of the clinical study report. The Investigator(s) will be provided reasonable access to statistical results and tables and will be provided a summary of the study results.

7.4 Interim Monitoring and Closeout

Interim monitoring and close-out visits may be conducted by the Sponsor for quality assurance.

8.0 Changes Necessary after Study Initiation

If there are changes to the study plan or protocol, these changes will be agreed upon by the Sponsor, its acting representative (if appropriate), the Investigator(s), and the IRB before the changes are implemented. All changes must be documented.

9.0 Study Completion

See section 3.4 for timeline details. Upon completion of the study, a study exit form will be completed for each patient.

10.0 Confidentiality/Publication of the Study

Any information shared by the Sponsor regarding this clinical study is the property of the Sponsor. This protocol is considered proprietary information and should be kept confidential.

The data generated by this clinical study are the property of the Sponsor. These data may be used by the Sponsor, now and in the future, for presentation or publication at the Sponsor's discretion or for submission to regulatory agencies.

Hill-Rom®	Evaluation of a practice change to include The MetaNeb® System to reduce postoperative pulmonary complications	Page 29 of 31
CBI	8 September 2016	Rev C Protocol #: CR-RR2015-001

**List of Abbreviations**

CPAP	Continuous Positive Airway Pressure
ICU	Intensive Care Unit
LOS	Length of Stay
MV	Mechanical Ventilation
NIV	Noninvasive Ventilation
OSA	Obstructive Sleep Apnea
PPC	Postoperative Pulmonary Complication
PSHA	Post-Surgical Hospital Admission

## 1 Introduction

The study will be conducted in two stages.

Stage I of the study, STANDARD THERAPY, is a retrospective review of medical records for 200 randomly selected post-surgical patients, who received standard of care therapy as defined by current hospital and respiratory care department policies and procedures. Data collected in Stage I will include data from the medical records of eligible patients treated during the year prior to the start of Stage II. This allows for inclusion of patients from the seasonally consistent time period as well as those from most recent time period, during which care practices are most similar between the 2 stages.

Stage II of the study, a CHANGE IN PRACTICE will be made and patients will receive standard care with the addition of therapy with The MetaNeb® System. Other standard airway clearance and lung expansion therapies typically delivered by Respiratory Therapy will not be delivered during Stage II. Data from approximately 200 patients will be collected from the medical records at 3 sites. However, an adjustment in sample size may be made based on the incidence rate for post-operative pulmonary complications in Stage I, to allow for a robust estimate and assessment of the effect of therapy with The MetaNeb® System.

Stage II will start after gathering and analysis of data from Stage I

## 2 STUDY OBJECTIVES AND ENDPOINTS

### 2.1 Primary Objective and Endpoint

The primary objective of Stage I of this study is to estimate the incidence of postoperative pulmonary complications (PPC) in post-surgical patients receiving standard of care per hospital and respiratory care department procedures and policies.

The primary objective of Stage II of this study is to estimate the incidence of PPC in post-surgical patients receiving change in practice therapy regimen, which includes the addition of the MetaNeb® System to the standard of care per hospital and respiratory care department procedures and policies.

The primary endpoint at each stage is to evaluate the proportion of subjects who experience a significant PPC within seven (7) days of: post-surgical hospital admission (Stage I) or post-surgical hospital admission and MetaNeb® System administration (Stage II). A PPC is defined as having one or more of the following:

- 1. Patient requires prolonged mechanical ventilation for > 24 hours**  
Invasive mechanical ventilation (MV) for > 24 hours from post-surgical hospital admission (PSHA)
- 2. Patient requires prolonged respiratory support for > 24 hours from PSHA**

- Requirement for non-invasive ventilation (NI V) or continuous positive airway pressure (CPAP) above patient's baseline requirement, not related to obstructive sleep apnea (OSA), for > 24 hours from PSHA
- Requirement for O2 therapy > 40 % FiO2 or > 5 LPM via NC (and above patient's baseline), for > 24 hours from PSHA

3. **Diagnosis of Pneumonia within 7 days from PSHA**
  - Physician documented pneumonia, and
  - Radiologists report indicating pneumonia / new or expanded infiltrate, and
  - Elevated or low Temperature (> 38° C or < 36° C, or as defined by the site) and/or elevated white count above the upper level of normal as defined by the site
4. **Readmission to ICU (or transfer to an elevated level of care) for pulmonary complications**  
Defined as readmission to the ICU or readmission to an elevated care unit within 7 days from PSHA

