3.2 Study Population

The study population consists of adult post-surgical patients who have undergone thoracic, aortic or upper abdominal surgery who are at high risk for PPCs.

3.2.1 Inclusion Criteria:

Patients who meet all of the following criteria will be included in the study:

- Age \geq 18 years
- Post-thoracic, -upper abdominal or -aortic surgery
- Open surgical procedure
- Incision at or above the umbilicus
- High risk defined by:
 - Documented ASA class \geq 3

Hill-Rom®	Evaluation of a practice change to include The MetaNeb® System to reduce postoperative pulmonary complications			Page 16 of 31
	CBI	8 September 2016	Rev C	Protocol #: CR-RR2015- 001

OR

- Documented ASA class 2 **AND** One or more of the following:
 - Current Smoker or Smoking history within past 6 months
 - History of COPD
 - Documented Obesity and/or BMI $\geq 30 \text{ kg/m}^2$
 - Age ≥ 75

3.2.2 Exclusion Criteria:

Patients who meet any of the following criteria will be excluded (or will be exited) from the study:

- Contraindication to Continuous High Frequency Oscillation (CHFO) therapy (e.g. untreated tension pneumothorax)
- Minimally invasive or “...scopic” surgical procedure
- Spinal surgery involving a posterior approach
- Surgery for organ transplant
- Chronic invasive Positive Pressure Ventilation (PPV) therapy

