3.3 Evaluation Criteria/Effectiveness

The CHANGE IN PRACTICE therapy regimen (which includes therapy with The MetaNeb® System) will be evaluated to determine if there is a decrease in the number of patients who experience Significant Postoperative Pulmonary Complications among the group of patients treated with The MetaNeb® System. Endpoints are described below:

Primary Endpoint:

Significant Postoperative Pulmonary Complication (PPC):

One or more of the following that occurs within seven (7) days of the post-surgical admission will be considered a Significant Postoperative Pulmonary Complication (PPC)

- **Patient Requires Prolonged Mechanical Ventilation:**

Defined as patient requirement for invasive mechanical ventilation (MV) for > 24 hours (after hour 24) post-operatively. This includes patients that require re-intubation and MV after hour 24, regardless of length of time on MV in the first 24 hours postoperatively.

Hill-Rom®	Evaluation of a practice change to include The MetaNeb® System to reduce postoperative pulmonary complications	Page 17 of 31
CBI	8 September 2016	Rev C Protocol #: CR-RR2015-001

- **Patient requires prolonged respiratory support for > 24 hours from post-surgical admission**
 - Requirement for non-invasive ventilation (NIV) above patient's baseline requirement after hour 24, or continuous positive airway pressure (CPAP) above patient's baseline requirement after hour 24.
 - Requirement for O₂ therapy > 40 % FiO₂ or > 5 LPM via NC (and above patient's baseline) after hour 24 postoperatively.
- **Diagnosis of Pneumonia Within Seven (7) Days**
 - Physician documented pneumonia AND
 - Radiologists report indicating pneumonia / new or expanded infiltrate AND
 - Elevated or low Temperature (> 38° C or < 36° C, or as defined by the site) and/or elevated white count above the upper level of normal as defined by the site
- **Readmission to ICU (or transfer to an elevated level of care) for pulmonary complications within seven (7) days of the post-surgical hospital admission**

Defined as readmission to the ICU within seven days of post-surgical hospital admission or readmission to an elevated care unit such as special care or ICU step-down unit after being moved to a lower (e.g. general care) floor (e.g. patient discharged from ICU on day 4 at 0800 is readmitted to the ICU before day 8 at 0800).

Secondary Endpoints:

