### 6.1 Description of Analytical Methods

#### 6.1.1 Derived Variables

**Primary Endpoint:** occurrence of a postoperative pulmonary complication (PPC).

Stage I: during the 7 days post-surgery hospital admission (PSHA)

Stage II: during the 7 days PSHA. Event must occur after MetaNeb® administration.

For each subject, occurrence of a PPC will be set to yes if one or more of the four conditions below occur.

- i. **PPCflg1:** Patient Requires Prolonged Mechanical Ventilation beyond Hour 24 from PSHA.

Duration of invasive mechanical ventilation (IMV) is defined as IMV stop time minus IMV start time where:

IMV Start Time=date & time of the later of start of IMV or PSHA

IMV Stop Time=date & time of the earlier of stop of IMV or PSHA+7

If IMV is required on more than one occasion during the 7 days following PSHA, then the cumulative sum will be calculated.

$$\text{PPCflg1} = \begin{cases} 1 & \text{if the latest IMV stop time is more than 24 hours after PSHA} \\ 0 & \text{otherwise} \end{cases}$$

If IMV start date is available, but the start time is missing, then a clock time consistent with the earliest possible time of the day will be imputed, ex. Hour 00.00 or PSHA clock time.

If the IMV stop date is available, but the stop time is missing, then the IMV stop time will be taken as the assessment time.

- ii. **PPCflg2:** Patient Requires Prolonged Respiratory Support beyond Hour 24 from PSHA

- a) Duration of non-invasive MV (NIMV) is defined as NIMV Stop time minus NIMV start time. NIMV start and stop times are defined similarly to those of IMV.

Imputations for missing NIMV start or stop times will be used similarly to those of IMV.

- b) Duration of CPAP is defined as CPAP Stop time minus CPAP Start time.

- c) Duration of O2 therapy [if >40% FiO2 or >5 LPM via Nasal Cannula] will be calculated similarly.

Duration of respiratory support is defined as the sum of durations of NIMV, CPAP, and O2 therapy during the 7 days following hospital admission.

$$\text{PPCflg2} = \begin{cases} 1 & \text{if the latest NIMV, CPAP, or O2 therapy stop time} \\ & \text{is more than 24 hours after PSHA} \\ 0 & \text{otherwise} \end{cases}$$

- iii. **PPCflg3:** Diagnosis of pneumonia

- iv. **PPCflg4:** Readmission to ICU (or transfer to an elevated care) for PPC with 7 days of PSHA

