### **6.1.6 Pre-Surgery Respiratory Status**

Pre-surgery status of invasive mechanical ventilation, non-invasive mechanical ventilation, CPAP, and supplemental oxygen will be tabulated.

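### The ventilation and pneumonia components of the primary endpoint lack the baseline condition that component 2 has, so some conditions present before surgery can be scored as new complications

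*SAP*

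**What the plan says.** **Component 1, invasive ventilation.** SAP 2.1 defines it as "Invasive mechanical ventilation (MV) for > 24 hours from post-surgical hospital admission (PSHA)". Protocol 3.3 has "Defined as patient requirement for invasive mechanical ventilation (MV) for > 24 hours (after hour 24) post-operatively" and adds re-intubation after that hour. Neither refers to the patient's state before surgery. SAP 6.1.1 sets "IMV Start Time=date & time of the later of start of IMV or PSHA" and gives PPCflg1 the value 1 "if the latest IMV stop time is more than 24 hours after PSHA".

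**Component 2, respiratory support.** Protocol 3.3 and SAP 2.1 both restrict it to support above the patient's own baseline. The PPCflg2 derivation in SAP 6.1.1 does not restate this.

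**Component 3, pneumonia.** SAP 2.1 heads it "Diagnosis of Pneumonia within 7 days from PSHA". Three things are required: a physician's diagnosis, a radiology report, and a temperature or white-count sign. The radiology criterion reads "Radiologists report indicating pneumonia / new or expanded infiltrate AND". In SAP 6.1.1, PPCflg3 is named as a diagnosis of pneumonia, with no onset rule.

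**Exclusions and baseline data.** The only related exclusion in Protocol 3.2.2 is "Chronic invasive Positive Pressure Ventilation (PPV) therapy". Protocol 3.4.1 records respiratory status before surgery, and SAP 6.1.6 says "Pre-surgery status of invasive mechanical ventilation, non-invasive mechanical ventilation, CPAP, and supplemental oxygen will be tabulated". The field enters no endpoint flag. Pneumonia is not a named item in the medical history (Protocol 3.4.1, SAP 6.1.5); it could appear only under other pulmonary conditions.

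**The concern.** The objective is the incidence of postoperative complications, and the study attributes a difference between stages to the device (Protocol 3.5.2). A condition already present when the patient goes to theatre is not an incident complication. If such cases are scored equally often in both stages, they dilute a real effect. If they are scored more often in one stage, they create or hide a difference unrelated to the device. SAP 6.3 plans proportions with confidence intervals and no baseline adjustment, so an imbalance would pass straight into the comparison. The Stage I rate may also be used to adjust the sample size (Protocol 3.1.2, SAP 1), so the same cases would inflate that input.

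**Working it through.** The plan has no figure to reproduce here; SAP 5 states that no formal sample size determination was made. The check is a reading of the definitions, followed by an illustration of scale.

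**Step 1: component 1.** Take a patient acutely ventilated before surgery.
- The patient is eligible, because only chronic invasive ventilation is excluded. The ITT population in SAP 6.2 enforces that exclusion and nothing further on ventilation.
- The start-time rule moves the beginning of ventilation to post-surgical admission. It does not remove ventilation that began earlier.
- The flag looks only at the last stop time. If that is later than hour 24, PPCflg1 = 1; if ventilation ends before hour 24 and is not resumed, PPCflg1 = 0.

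**Step 2: component 3.** Take a patient operated on with active pneumonia.
- This is not an exclusion.
- The radiology criterion offers alternatives separated by a slash. A new or enlarged infiltrate satisfies it, but so does a report that simply indicates pneumonia.
- If the postoperative notes, film and temperature or white count still show the illness within seven days, all three criteria are met.

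**Step 3: are the stages treated alike?** Two features apply to Stage II only.
- SAP 2.1 and 6.1.1 require the Stage II event to follow MetaNeb administration. They do not say how a condition already under way at first use is dated, so it might count in Stage I and not in Stage II.
- Consent is needed in Stage II and waived in Stage I (Protocol 5.1), and is scheduled before surgery (Protocol Table 1). Intubated patients may therefore be under-represented in Stage II. That is an inference; the documents do not state it.

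**Step 4: illustration of scale.** Let p be the incident rate and q the share of patients scored only because of a pre-existing condition. Observed rate = q + (1 − q) × p.

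Inputs: p = 10% in Stage I, the middle of the 5%–15% in Protocol 3.5.1. The assumptions are a true 30% relative reduction (Stage II p = 7%), no device effect on pre-existing cases, and q = 1%, 3% or 5% (2, 6 or 10 of 200 patients).

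| q | Stage I | Stage II | Observed relative reduction |
|---|---|---|---|
| 1% | 0.01 + 0.99 × 0.10 = 10.90% | 0.01 + 0.99 × 0.07 = 7.93% | 1 − 7.93/10.90 = 27.2% |
| 3% | 0.03 + 0.97 × 0.10 = 12.70% | 0.03 + 0.97 × 0.07 = 9.79% | 1 − 9.79/12.70 = 22.9% |
| 5% | 0.05 + 0.95 × 0.10 = 14.50% | 0.05 + 0.95 × 0.07 = 11.65% | 1 − 11.65/14.50 = 19.7% |

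Power, with 200 per stage, two-sided 5% (SAP 6), normal approximation, and an assumed halving of the incident rate:

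| True rates | q = 0 | q = 1% | q = 2% | q = 5% |
|---|---|---|---|---|
| 5% vs 2.5% | 25.9% | 21.4% | 18.3% | 13.3% |
| 10% vs 5% | 47.5% | 42.9% | 39.1% | 30.6% |
| 15% vs 7.5% | 66.1% | 62.4% | 58.9% | 50.0% |

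**Step 5: the extreme.** Suppose pre-existing cases are scored in Stage I only and the device does nothing. With p = 10%, the apparent reduction is 1 − 10.0/10.9 = 8.3% at q = 1%, 1 − 10.0/12.7 = 21.3% at 3%, and 1 − 10.0/14.5 = 31.0% at 5%. The two-sided rejection probability, nominally 5%, is 6.0% at q = 1%, 8.9% at 2% and 27.8% at 5%. At q = 5% it is 44.3% if p = 5% and 20.3% if p = 15%.

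**The case against.** The strongest case against has five parts.

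- **Not every pre-existing case is scored.** A reader might infer that anyone ventilated or with pneumonia before surgery is counted. The documents do not support that: chronic ventilation is excluded, other ventilated patients count only if ventilated after hour 24, and pneumonia needs all three criteria. This stands, and the point is limited accordingly.
- **The wording leans towards new events.** Protocol 3.3 speaks of a component that occurs within seven days, Protocol 3.4.1 treats pneumonia diagnosis as a daily milestone, and the radiology criterion mentions newness. This stands in part. The wording suggests onset after surgery without requiring it, and the PPCflg1 formula points the other way.
- **Such patients may be rare.** A field on a baseline form does not show that acutely ventilated patients are expected. Nor does the clause on time on mechanical ventilation (Protocol 3.3) about intubation in place before surgery started, since it may cover routine anaesthetic intubation. This stands: the number is unknown.
- **The device might help patients already ventilated.** Protocol 1.2 reports better weaning in a long-term-care series. This stands. A zero effect in these patients is an assumption of the illustration, and it is a reason to report the present flag as a sensitivity analysis.
- **The plan already shows some of this.** Preoperative ventilation is tabulated and each component's incidence is presented (SAP 6.3). That would reveal an imbalance in ventilation but not correct the composite, and it does not reliably capture preoperative pneumonia.

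**Conclusion.** The concern holds in a limited form. Components 1 and 3 lack a baseline condition, although the plan applies that principle in defining component 2. The chronic-ventilation exclusion and the infiltrate wording close the gap only in part. The Stage II-only timing rule, and possibly consent, may make it unequal between stages.

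The size of the bias cannot be derived from the documents. With equal shares of 1% to 5%, the dilution runs from small (30% seen as 27%) to material (30% seen as 20%). The 31% apparent benefit of an inert device needs the highest assumed share, every case in Stage I and none in Stage II; it is a bound, not an expectation. A reader might infer that a favourable result would be an artefact of prevalent cases. Nothing in the documents establishes that. The change is worth making because it is cheap and removes a source of bias that the planned analysis does not correct.

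**What to change.** Amend Protocol 3.3, SAP 2.1 and SAP 6.1.1, with identical wording for both stages.

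1. **Ventilation.** Use the preoperative invasive-ventilation field already collected. Ventilation that continues unbroken from before surgery should not by itself set PPCflg1 or the 48-hour ventilation endpoint; re-intubation after extubation still counts. State that intubation for the anaesthetic is not preoperative ventilation. Keep these patients in the denominator, since they remain at risk of the other components. Report their number by stage. As sensitivity analyses, give the result with the flag as now written and the result with these patients left out.
2. **Pneumonia.** Record by chart review whether pneumonia was active at the time of surgery. Tying the item to active disease keeps a long-resolved episode from barring a genuine new event. In patients with active pneumonia, count component 3 only if the postoperative report meets the new-or-expanded alternative of the radiology criterion.
3. **Stage II timing.** Say how a condition already present at first device use is classified, so that the baseline rule works the same way in both stages.

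Cost: one extra chart item in each stage, a little more analysis, and a slightly lower event count.
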